6.4.1. Unblinding

Treatment assignment may be unblinded if knowing the patient's treatment assignment would affect immediate medical management of the patient. The IWRs will be programmed with blind-breaking instructions. In case of an emergency, the Investigator has the sole responsibility for determining if unblinding of a patient's intervention assignment is warranted. Patient safety must always be the first consideration in making such a determination. If the Investigator decides that unblinding is warranted, the Investigator should make every effort to contact the Sponsor prior to unblinding a patient's intervention assignment unless this could delay emergency treatment of the patient. If a patient's intervention assignment is unblinded, the Sponsor must be notified within 24 hours after breaking the blind. The date and reason that the blind was broken must be recorded in the source documentation and case report form, as applicable.

Any unblinding of Sponsor personnel for expedited reporting of suspected unexpected serious adverse reactions (SUSARs) or other reasons including planned interim analyses will be addressed in a separate plan.

6.4.2. Patient Enrollment and Study Drug Assignment

It is the responsibility of the Investigator to ensure that patient eligibility is confirmed prior to randomization. Documentation of the personally signed and dated informed consent of each patient, using the study-specific ICF, is required before initiating the Screening Period.

After written informed consent has been obtained, the patient's identification number will be obtained from the IWRS. Once eligibility to participate has been established, the randomized treatment assignment will be obtained from the IWRS.

6.5. Study Drug Compliance

Patients will be dispensed study drug during their study visits and will self-administer study drug at home. Patients must be in fasted state for at least 8 hours prior to study drug administration. At all study visits, study drug administration will be observed at the study site. Patients should be instructed to hold their dose of study drug on visit days until all visit procedures have been completed. On all other days, patients will self-administer the study drug orally once daily in the morning on an empty stomach, after an 8 hour fast.

Compliance will be assessed by direct questioning and counting returned capsules during the study visits and documented in the source documents and electronic case report form (eCRF). Deviations from the prescribed dosage regimen should be recorded in the eCRF.

If a patient is required to be quarantined due to active infection of COVID-19 or exposure to COVID-19, or is otherwise unable to visit the site due to COVID-19, study drug may be mailed to the patient or made available via another appropriate mechanism (i.e., curbside pickup, etc).

Patients will be asked to maintain records of self-administered drug on non-study visit days. A record of the number of study drug capsules dispensed to and taken by each patient must be maintained and reconciled with study drug and compliance records at the site. Study drug start and stop dates, including dates for delays will also be recorded in the eCRF.

6.6. Concomitant Therapy

Any medication or vaccine (including over-the-counter or prescription medicines, vitamins and/or herbal supplements) that the patient is receiving at the time of randomization or receives during the study must be recorded at each study visit along with:

- Reason for use
- Dates of administration including start and end dates
- Dosage information including dose and frequency

Medications prohibited from randomization through end of study follow-up:

- Monoamine oxidase inhibitors including isoniazid, linezolid, methylene blue, tranylcypromine, isorboxazid, phenelzine, selegiline, rasagiline, safinamide
- Medications with potential impact on NASH outcome, including obeticholic acid, pioglitazone or other PPAR γ agonists, or high-dose vitamin E (> 400 IU/day)
 - Patients receiving \leq 400 IU/day prior to study should not have dose adjustment on-study
- Medications potentially impacting steatohepatitis, including but not limited to systemic corticosteroids (prednisone equivalent of > 10 mg/day for > 2 weeks), amiodarone, tamoxifen, and methotrexate. Use of systemic corticosteroids for < 2 weeks within 3 months prior to randomization and while on study is allowed.
- Oral creatine supplementation
- Potent inducers or inhibitors of CYP3A; a noncomprehensive list for known CYP3A strong inducers and inhibitors is provided below:
 - Potent CYP3A inhibitors prohibited on study include but are not limited to: boceprevir, cobicistat, ritonavir, grapefruit juice, itraconazole, ketoconazole, posaconazole, telaprevir, telithromycin, troleandomycin, voriconazole, clarithromycin, idelalisib, nefazodone, and neflunavir
 - Potent CYP3A inducers prohibited on study include but are not limited to: apalutamide, carbamazepine, enzalutamide, mitotane, phenytoin, rifampin, and St. John's wort
 - Patients who require initiation of potent CYP3A inducers and inhibitors during the study should discontinue study drug. For patients who subsequently discontinue prohibited medications, study drug administration may not be resumed unless discussed with the Medical Monitor. Patients who do not resume study drug should continue in the study for Follow-Up.
- Other investigational agents

All other medications not listed above are acceptable for use from randomization through end of study follow-up. The Medical Monitor should be contacted if there are any questions regarding concomitant therapy.

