7. Albumin $< 3.3 \text{ g/dL}$
8. International normalized ratio (INR) > 1.3
9. Alkaline phosphatase (ALP) $> 159 \text{ IU/L}$
10. Platelet count $< 150,000 / \text{mm}^3$
11. eGFR $< 60 \text{ mL/min}/1.73\text{m}^2$
12. Weight loss of $> 5\%$ total body weight within 3 months prior to Screening
13. History of a malignancy within 2 years of Screening, with the following exceptions:
 - a) Adequately treated carcinoma in situ of the cervix
 - b) Adequately treated basal or squamous cell cancer or other localized non-melanoma skin cancer
14. Uncontrolled diabetes with hemoglobin A1c (HbA1c) $> 9.5\%$ or actively undergoing anti-diabetes medication titration (see Exclusions 35, 36, and 39 for additional details).
Note: Patients with or without diabetes may be enrolled provided all eligibility criteria are met.
15. Average weekly alcohol consumption of > 21 standard drinks for males and > 14 standard drinks for females over a period of more than 3 consecutive months in the year prior to Screening. Remote history of alcoholism with abstinence > 12 months prior to Screening and no history of alcoholic liver disease is permissible.

Note: A standard drink is defined as 12 oz (360 ml) beer, 1.5 oz (45 ml) liquor, or 5 oz (150 ml) wine.

16. Illicit substance/chemical abuse in the 12 months prior to Screening
17. Cannabis use (tetrahydrocannabinol [THC] and cannabidiol [CBD]) within 14 days of randomization
18. Unwilling to abstain from excessive alcohol use (defined in #15 above), cannabis use, and illicit substance use during study participation
19. Positive for human immunodeficiency virus (HIV) infection
20. QTcF > 450 ms for males, > 470 ms for females
21. Unstable cardiovascular disease defined as myocardial infarction, unstable angina, percutaneous intervention, coronary artery bypass graft, or stroke within 6 months prior to randomization
22. New York Heart Association class III or IV heart failure, or know left ventricular ejection fraction < 30%
23. Uncontrolled hypertension defined as systolic blood pressure > 160 mmHg or a diastolic blood pressure > 100 mmHg (treated or untreated) on at least two occasions more than 10 minutes apart
24. History of hypotension including orthostatic or postprandial hypotension
25. History of seizure disorder
26. History of known or suspected serotonin syndrome
27. Schizophrenia or bipolar disorder
28. Parkinson's disease
29. Known or suspected pheochromocytoma
30. Known allergy to study drug

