31. Clinically significant multiple or severe drug allergies, or severe post-treatment hypersensitivity reactions
32. Laboratory or clinical evidence of current infection with Severe Acute Respiratory Syndrome Coronavirus 2 (SARS-CoV-2), i.e., COVID-19

33. Presence of any condition that could, in the opinion of the Investigator, compromise the patient's ability to participate in the study

Prior Therapy

34. Use within 6 months prior to Screening: Treatment with monoamine oxidase inhibitors including but not limited to isoniazid, linezolid, methylene blue, tranylcypromine, isorboxazid, phenelzine, selegiline, rasagiline, safinamide; these therapies are also prohibited from randomization through end of study follow-up per [Section 6.6](#)

35. Use within 3 months prior to Screening: obeticholic acid, pioglitazone or other PPAR γ agonists, or high-dose vitamin E (> 400 IU/day); these therapies are also prohibited from randomization through end of study follow-up per [Section 6.6](#)

36. Initiation or dose adjustment within 3 months prior to Screening (i.e., must be on stable dose for 3 months prior to Screening):

- GLP-1 analogues, DPP-4 inhibitors, and SGLT2 inhibitors
- Vitamin E ≤ 400 IU/day

37. Use within 3 months prior to Randomization:

- Medications potentially impacting steatohepatitis, including but not limited to systemic corticosteroids (prednisone equivalent of > 10 mg/day for > 2 weeks), amiodarone, tamoxifen, and methotrexate; these therapies are also prohibited from randomization through end of study follow-up per [Section 6.6](#)

38. Initiation or dose titration within 3 months prior to Randomization:

- Hormonal contraceptives

39. Initiation or dose titration within 2 months prior to Randomization (i.e., must be on stable dose for 2 months prior to Randomization):

- Metformin and other antidiabetic drugs not described above.

40. Use within 2 weeks prior to Randomization:

- Oral creatine supplementation; this is also prohibited from randomization through end of study follow-up per [Section 6.6](#)
- Vaccination for influenza, COVID-19, or other routine vaccinations
- Potent CYP3A inducers or inhibitors; these therapies are also prohibited from randomization through end of study follow-up per [Section 6.6](#)

Prior Clinical Study Experience

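### Antidiabetic drugs must be stable at entry, but Protocol 6.6 keeps only low-dose vitamin E stable on study, so elective antidiabetic starts and dose changes after randomization are permitted

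*Protocol*

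**What the plan says.** Protocol 5.2 sets two entry rules for antidiabetic drugs.

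- Exclusion 36 reads "Initiation or dose adjustment within 3 months prior to Screening (i.e., must be on stable dose for 3 months prior to Screening". It covers "GLP-1 analogues, DPP-4 inhibitors, and SGLT2 inhibitors" and, in the same item, "Vitamin E ≤ 400 IU/day".
- Exclusion 39 requires a stable dose for 2 months before Randomization. It covers "Metformin and other antidiabetic drugs not described above".

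Exclusion 14 also bars patients who are "actively undergoing anti-diabetes medication titration (see Exclusions 35, 36, and 39 for additional details".

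Protocol 6.6 lists the drugs prohibited on study. The only antidiabetic drugs among them are pioglitazone and other PPAR-gamma agonists, which come from Exclusion 35. For low-dose vitamin E it adds that patients on no more than "400 IU/day prior to study should not have dose adjustment on-study". It then closes the list: "All other medications not listed above are acceptable for use from randomization through end of study follow-up". Reason for use, start and end dates, dose and frequency are recorded for every drug.

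SAP 7.5 tabulates prior and concomitant medications separately, by arm, at ATC level 2, ATC level 4 and preferred name. SAP 7.2 counts antidiabetic drugs by arm at baseline.

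**The concern.** The entry criteria treat a recent antidiabetic start or dose change as reason enough to exclude a patient. The same event the day after randomization is allowed, and it falls inside the interval over which change in cT1, liver fat, ALT and weight is measured. Two members of the same exclusion item, low-dose vitamin E and the three incretin/SGLT2 classes, are handled differently after randomization, and no reason is given.

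At stake is the clarity of the preliminary efficacy readout. An elective antidiabetic change may move these endpoints for reasons unrelated to TERN-201, and with 10 to 20 patients per arm a few such patients can fall unevenly by chance.

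A smaller gap lies before randomization. Exclusion 36 looks back from Screening, whereas Exclusion 39 looks back from Randomization. The Schedule of Activities takes the pre-treatment MRI at Screening only, so a drug started after that scan would act within the measured change from baseline.

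**Working it through.** **Step 1. Entry rule against on-study rule.**

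| Drug | Entry rule (Protocol 5.2) | On-study rule (Protocol 6.6) |
|---|---|---|
| PPAR-gamma agonists | 35: no use in the 3 months before Screening | Prohibited |
| Vitamin E, 400 IU/day or less | 36: stable 3 months before Screening | No dose adjustment |
| GLP-1, DPP-4, SGLT2 | 36: stable 3 months before Screening | Not mentioned, so acceptable |
| Metformin, other antidiabetics | 39: stable 2 months before Randomization | Not mentioned, so acceptable |

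Exclusions 34, 35, 37 and parts of 40 state that the restriction continues on study under 6.6. Exclusions 36 and 39 do not. The 6.6 item on drugs with potential impact on NASH outcome cannot be stretched to GLP-1 or SGLT2 drugs: it bans use outright, and Exclusion 36 admits stable users.

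**Step 2. What the planned tables show.** SAP 7.5 classes a drug ongoing at first dose as both prior and concomitant. For a given preferred name and arm, leaving aside patients who stop and restart:

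concomitant count − prior count = new starters − patients who stopped before first dose.

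New starts are thus visible only as a net figure. Repeat records of one preferred name count once per patient, so dose changes do not appear. They can be recovered from the listings.

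**Step 3. Size.** The plan states no figure to reproduce, and the sample size has no power basis. The documents give no diabetes prevalence, change rate, drug effect or SD. Arm sizes (Protocol 4.1; SAP 4.6) are 10 placebo and 20 active in Part 1, and about 20 v 20 if Part 2 enrols and placebo is pooled. Everything else below is an assumption.

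(a) *Responder tables* (cT1 decrease of 80 msec, relative liver fat decrease of 30%, weight decrease of 5%). One patient crossing a threshold moves the percentage by 1/10 = 10 points or 1/20 = 5 points.

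(b) *Two changers among the 30 Part 1 patients*, hypergeometric:

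- 0 placebo, 2 active: 190/435 = 0.437, gap 10 points
- 1 and 1: 200/435 = 0.460, gap 5 points
- 2 placebo, 0 active: 45/435 = 0.103, gap 20 points

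Mean absolute gap = 0.437×10 + 0.460×5 + 0.103×20 = 8.7 points. The gap is at least 10 points with probability 0.540 but exceeds 10 with probability only 0.103, because 0/10 v 2/20 is exactly 10.

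(c) *Common change rate p in every arm*, independent binomials; SD of gap = √[p(1−p)(1/n₁+1/n₂)]:

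| p | SD, 10 v 20 | P(gap > 10 points) | SD, 20 v 20 | P(gap > 10 points) |
|---|---|---|---|---|
| 5% | 8.4 points | 0.112 | 6.9 points | 0.067 |
| 10% | 11.6 points | 0.268 | 9.5 points | 0.180 |
| 15% | 13.8 points | 0.362 | 11.3 points | 0.263 |

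These are gaps in the proportion of patients who changed treatment, not in an outcome.

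(d) *Effect on a mean difference.* Suppose each change shifts relative liver fat by 10 to 30 points. The added SD in the difference runs from 0.069×10 = 0.7 points (5%, 20 v 20) to 0.138×30 = 4.1 points (15%, 10 v 20), centred on zero. It combines in quadrature with the ordinary standard error. For 10 v 20 and an assumed SD of 20, 30 or 40 points, that standard error is SD×√(1/10+1/20) = 7.7, 11.6 or 15.5. The 4.1-point case raises it by 13.4%, 6.2% or 3.5%; for example √(7.75²+4.15²)/7.75 = 1.134. At a 5% rate and a 10-point effect (added SD 0.8), the rise is 0.6% or less.

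**The case against.** The best defence is that this is a choice. Exclusion 38 (hormonal contraceptives) is also entry-only; the vitamin E line can be read as keeping low-dose users below the prohibited dose; and a trial that admits HbA1c up to 9.5% may reasonably leave diabetes care free. Part of this stands: needed care should not be restricted. The threshold reading is incomplete, though, because the vitamin E line rules out any dose adjustment, not only one that crosses 400 IU/day.

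The second defence is that the consequence is small and already accounted for. Extra variability enters the residual variance, and so the planned standard errors and the 90% and 95% intervals. One patient being worth 10 points is a property of n = 10, and the planned Clopper-Pearson intervals show it. Both statements are correct and are why the priority is low.

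On the screening gap, Exclusion 14 bars active titration, and "It is the responsibility of the Investigator to ensure that patient eligibility is confirmed prior to randomization". What remains is a fixed-dose start that Exclusion 36, as worded, does not clearly reach.

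Three stronger readings are tempting and are not supported.

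- A reader might infer bias in favour of or against TERN-201. Assignment is randomized and double-blind; under the equal change rates and effects assumed above, the expected shift is zero.
- A reader might infer that antidiabetic changes are lost or wholly absent from the by-arm tables. Dates and doses are collected, SAP 4.3 lists all case report form data, and SAP 7.5 shows new starts indirectly.
- A reader might infer that the trial's main conclusions are affected. The endpoints concerned are exploratory or added by the SAP, and SAP 8.6 calls all testing nominal.

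**Conclusion.** The point holds as a minor design improvement. Protocol 6.6 expressly permits elective antidiabetic changes that the entry criteria treat as disqualifying, and Exclusion 36 leaves a narrow opening during screening. The result is avoidable noise and possible chance imbalance in cT1, liver fat, ALT and weight. The primary safety and secondary PK/PD objectives are not touched.

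The size cannot be fixed from the documents. Under the assumed 5% to 15% change rates and 10 to 30 point effects, the increase in standard error for a 10 v 20 liver fat comparison ranges from negligible to about 13%; the upper end needs the highest rate, the largest effect and the smallest SD together. The HbA1c limit, the bar on active titration at entry and the 12-week treatment period all point to a low frequency of changes.

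**What to change.** **Protocol 6.6**, beside the vitamin E line, add: *Antidiabetic drugs should not be started or dose-adjusted from randomization through Week 12 except when medically needed; any change is recorded and the patient remains in the study.*

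**Protocol 5.2, Exclusion 36**: run the stability window from 3 months before Screening through Randomization. Exclusion 39 already ends at Randomization.

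The cost is one short protocol amendment with IRB approval, which can be combined with the next amendment made for other reasons. The benefit is limited: the medical-need exception means that only elective changes are prevented. No needed care is restricted and no patient is removed.

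**Optional reporting aid, not a correction.** Report by arm the number of patients with a post-randomization start or dose change in the WHODD grouping for drugs used in diabetes, which SAP 7.2 already uses at baseline. SAP 7.5 shows new starts only indirectly and dose changes not at all. This is one table from data already collected and needs no amendment; it is best defined before the Part 1 lock and unblinding described in SAP 8.3. It changes no result. An analysis that drops or censors patients who changed treatment is not requested, because it would condition on a post-randomization event.

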6.7. Dose Modifications

Dose modifications of study drug are not permitted.

6.8. Dose Interruptions

On all non-study visit days, patients will self-administer the study drug orally once daily in the morning, on an empty stomach, after an 8 hour fast. If a patient forgets to self-administer study drug in the morning on a given day, the dose can be taken on the same day when the patient remembers, with the exception below:

- For patients participating in the PK/PD sub-study, drug must be self-administered the morning of the day prior to the Week 6 and Week 12 visits. If not, the visit should be rescheduled for the following day.

If a patient forgets to self-administer study drug on a given day, it will be designated a missed dose. Dosing may continue orally once daily according to the protocol schedule after a missed dose.

If study drug is discontinued or suspended for safety reasons considered related to study drug, dosing should not be resumed without consultation with the Medical Monitor. Information on stopping study drug for patients due to safety/other reasons is detailed in [Section 7](#).

6.8.1. Dose Interruptions due to COVID-19

If a patient requires home quarantine due to SARS-CoV-2 infection or exposure, or due to COVID-19 symptoms, the patient may continue study drug provided that appropriate safety follow-up is possible, and that hospitalization is not required. Home health care visits may be conducted to continue study assessments in the patient's home where feasible, and/or remote visits via telephone, telemedicine, or other appropriate virtual communication may be substituted for a visit to the site. Sites should discuss the mechanism for safety follow-up with the Medical Monitor.

If a patient has symptoms of COVID-19 requiring hospitalization, study drug must be discontinued during hospitalization. A case-by-case assessment of whether to resume study drug can be done upon discharge. Dosing should not be resumed without consultation with the Medical Monitor. The patient should be encouraged to remain in the study to be evaluated during the Follow-Up Period.

6.9. Intervention after the End of the Study

No further interventions are planned after the end of the study.

7. Discontinuation of Study Drug and Patient Discontinuation/Withdrawal

7.1. Discontinuation of Study Drug

Study drug must be discontinued for an individual patient in the following instances:

- If an AE of Grade 3 or above (National Cancer Institute (NCI) CTCAE 5.0) occurs and is considered related to study drug as judged by the Investigator per the guidance in [Appendix 6](#)
- Symptoms of COVID-19 requiring hospitalization
- Change in clinical status that, in the judgement of the Investigator compromises the patient's ability to continue treatment or is not considered to be in the patient's best interest
- Patient request to discontinue study drug for any reason
- Pregnancy during the study (refer to [Appendix 7](#))
- Sponsor discretion
- Discontinuation of the study at the request of the Sponsor, a regulatory agency, or Institutional Review Board (IRB)/Independent Ethics Committee (IEC)

Resumption of study drug may be considered in discussion with the Medical Monitor and Sponsor.

If one of the following situations occurs and is considered related to the study drug without alternative etiology, study drug may be discontinued at the discretion of the Investigator and the Medical Monitor should be informed (with repeat test performed within 48-72 hours once initial abnormality is detected):

- ALT or AST $> 8 \times$ ULN
- ALT or AST $> 5 \times$ ULN for more than 1 week, confirmed with a repeat assessment
- ALT or AST $> 2 \times$ Baseline with the appearance of fatigue, nausea, vomiting, right upper quadrant pain or tenderness, fever, rash, and/or eosinophilia $> 5\%$
- ALT or AST $> 2 \times$ Baseline and total bilirubin $> 2 \times$ ULN or INR > 1.5 for more than 1 week, confirmed with a repeat assessment

In addition, Investigators may permanently discontinue study drug at their discretion due to patient non-compliance with study drug or study assessments.

If study drug is permanently discontinued, the patient will remain in the study to be evaluated during the Follow-Up Period. See the Schedule of Activities for data to be collected at the time of discontinuation of study drug and follow-up and for any further evaluations that need to be completed.

